1.5.1.4 Potential Class-Related Ocular Risks Associated with Corticosteroid Therapies for the Treatment of Ocular Inflammation and Pain after Ocular Surgery

The active ingredient in APP13007, ■■■, is a potent corticosteroid so it has the following anticipated ocular risks associated with the corticosteroid class:

- Intraocular pressure (IOP) increase – prolonged use may result in glaucoma with damage to the optic nerve, defects in visual acuity and field of vision.
- Cataracts – Prolonged use ■■■ may result in posterior subcapsular cataract formation in the non-operated eye.
- Delayed healing – Use ■■■ after cataract surgery may delay healing and increase the incidence of bleb formation. In those diseases causing thinning of the cornea or sclera, perforations have been known to occur with the use of topical corticosteroids.
- Risk of Infection
 - Bacterial infections – Prolonged use ■■■ may suppress the host immune response and thus increase the hazard of secondary ocular infections. In acute purulent conditions, corticosteroids may mask infection or enhance existing infection.
 - Viral infections – Use of ocular corticosteroids may prolong the course and may exacerbate the severity of many viral infections of the eye (including herpes simplex).
 - Fungal Infections – Fungal infections of the cornea are particularly prone to develop coincidentally with long-term local corticosteroid application. Fungus invasion must be considered in any persistent corneal ulceration while a subject is participating in this clinical trial.

In clinical studies evaluating the use of corticosteroids after ocular surgery, ocular adverse reactions that occurred in 5% to 15% of subjects included corneal edema, ciliary and conjunctival hyperemia, eye pain, photophobia, posterior capsule opacification, anterior chamber cells, anterior chamber flare, conjunctival edema, and blepharitis. Other ocular adverse reactions occurring in 1% to 5% of subjects included reduced visual acuity, punctate keratitis, eye inflammation, and iritis. Ocular adverse reactions occurring in less than 1% of subjects included application site discomfort or irritation, corneal pigmentation and striae, episcleritis, eye pruritus, eyelid irritation and crusting, foreign body sensation, increased lacrimation, macular edema, sclera hyperemia, and uveitis. Most of these reactions may have been the consequence of the surgical procedure.

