Delayed Healing	
Subjects with thinning of the cornea or sclera are excluded because of the greater risk of perforations with the use of topical steroids.
 
Protocol includes stopping criteria for study drug if the Investigator, in consultation with the Study Medical Monitor, is concerned about delayed healing.
	
Use of APP13007 may delay healing after cataract surgery and increase the incidence of bleb formation. There were no reports of delayed healing after cataract surgery in Study CPN-201.

Potential Risk	Management	Comments
Risk of Infection	
Subjects with on-going ocular bacterial, viral or fungal infections are excluded from the study.
 
Ocular infections occurring during the study should be assessed and treated appropriately.
 
The Investigator should discuss with the Study Medical Monitor whether to stop study drug if ocular infection occurs.
	
Use of APP13007 may suppress the host immune response and increase the hazard of ocular infections. This risk is likely to be low based on data from studies of other steroids products approved for the treatment of inflammation and pain after ocular surgery.

Hypothalamic-Pituitary-Adrenal Axis (HPA) Suppression	
Monitor for symptoms and signs of reduced adrenal function (including fatigue, muscle weakness, loss of appetite and weight, abdominal pain, nausea and diarrhea, low blood pressure, depression and irritability, salt craving and hypoglycemia).
 
The Investigator should discuss with the Study Medical Monitor who will then discuss with the Sponsor whether to stop study drug.
	
While systemic absorption of topical corticosteroids can produce reversible HPA axis suppression with the potential for glucocorticoid insufficiency after withdrawal from treatment, this risk is likely to be very low
 
[REDACTED]
 
[REDACTED]
 
[REDACTED]
 
[REDACTED]
 
[REDACTED]
 
Nevertheless, Investigators should be aware that the symptoms and signs of reduced adrenal function can be nonspecific and they should remain alert to the possibility that this may occur.

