4.3 EXCLUSION CRITERIA

Participants will be excluded if they meet any of the following criteria:

1. Have a known sensitivity or allergy to [REDACTED] corticosteroids, or any of the study medication's components including [REDACTED]

█ or any routine medication required during cataract surgery or for the conduct of study procedures.

2. Have an ACC count > 0 or any evidence of intraocular inflammation (e.g., flare) in either eye at the Screening visit.
3. Have a Grade > 0 on the Ocular Pain Assessment in either eye at the Screening visit.
4. Have an immunosuppressive or autoimmune disease that in the opinion of the Investigator could affect intraocular inflammation or the normal healing process of the eye.
5. Have active or chronic/recurrent ocular or systemic disease that is uncontrolled and could affect wound healing and/or resolution of inflammation after cataract surgery.
6. Suspected or known malignancy or be currently receiving antineoplastic therapy. Note: subjects with basal cell carcinoma will not be excluded unless the Investigator believes that the condition has the potential to interfere with study procedures or analysis of results.
7. Are using certain medications, namely:
 - i. Subjects receiving treatment for macular degeneration (in either eye) with Eylea® (aflibercept), Avastin® (bevacizumab), Lucentis® (ranibizumab), Beovu® (brolucizumab-dbll) or Visudyne® (verteporfin) are excluded.
 - ii. PROKERA (preserved amniotic membrane) is excluded from 1 year prior to the Screening visit to the end of the study.
 - iii. Anti-inflammatory agents, analgesics (including opioids, narcotics, nonsteroidal anti-inflammatory drugs (NSAIDs), aspirin, acetaminophen and other pain medications) or immune-modulating agents systemically or in either eye from the beginning of the ‘Washout’ period in the List of Prohibited Medications ([Section 5.4.2](#)) until after the POD15 assessments, but preferably until after the POD22 assessments. *Note: (i) acetaminophen is permitted on the day of surgery; (ii) immunizations/vaccinations are permitted before and during the study.*

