 - iv. Use of any of the prohibited medications listed [Section 5.4.2](#) within a time period prior to surgery that is less than the minimum ‘washout’ period noted in Table 4. [NOTE: (i) These medications may not be used from the beginning of the ‘Washout’ period in Table 4 until after the POD15 assessments, but preferably until after the POD22 assessments; NOTE: (ii) Medications for anesthesia related

to cataract surgery, ocular pain control and non-prostaglandin-based therapy for the treatment of raised intraocular pressure (IOP) are allowed on the day of surgery only]

v. Non-approved drugs or investigational products other than the study drug in this study are prohibited from 28 days before surgery until after the subject has been released from the study.

8. Have an IOP < 5 mmHg or > 22 mmHg in either eye or a difference of > 5 mmHg between the eyes at the Screening visit.

9. Have a history of documented and repeated elevated IOP or glaucoma.

10. History of herpes keratitis in the study eye.

11. Have active corneal abrasions or ulcers in the study eye.

12. Have active or a history of chronic or recurrent inflammatory eye disease (e.g., iritis, scleritis, uveitis, iridocyclitis, rubeosis iridis) in the study eye.

13. Have evidence of acute external ocular infections (bacterial, viral and/or fungal infections including vaccinia, varicella and other viral diseases of the cornea and conjunctiva); tuberculosis of the eye; intraocular infections, active chalazion, or uncontrolled severe blepharitis in the study eye.

14. Have corneal dystrophies, including corneal guttae and Fuchs' dystrophy, or dysthyroid ophthalmopathy in the study eye.

15. Have uncontrolled and clinically significant dry eye syndrome in the study eye (mild dry eye with the use of artificial tears is allowed).

16. Have proliferative diabetic retinopathy, significantly compromised macular function; significant macular disease; have clinically-significant macular edema or a history of cystoid macular edema in the study eye; have cup:disc ratio > 0.8.

17. Have had corneal or retinal surgery (laser or incisional) in the study eye within 6 months of the Screening visit, or planning to have laser or incisional surgery during the study period in the study eye (other than cataract surgery).

18. Have ocular surgery planned, scheduled or performed on the contralateral eye within the 2 months prior to the surgery on the study eye.

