6.2.3 Visit 2 - POD1 (Day of Randomization)

Subjects will return to the clinic for the study visit on POD1 between 18 to 34 hours following conclusion of surgery on Day 0. This visit should be scheduled in the morning, as much as possible, to allow for administration of two doses of study drug during the day on POD1 for randomized subjects. However, if surgery is to be performed in the afternoon, subjects should still instill two doses of study drug on POD1 at least 6 hours apart.

All assessments will be performed as shown in the Schedule of Events (Table 1). Ocular assessments will be performed only on the operated, study eye.

The site will review eligibility criteria ([Section 4.2](#) and [Section 4.3](#)) to determine if the subject qualifies for randomization. Women of child-bearing potential must have a negative urine pregnancy test pre-randomization. If the subject meets all criteria, the subject will be randomized by site personnel using the EDC/IWRS system. The site should follow the instructions provided in the Study Reference Manual)/eCRF Completion Guidelines to enter appropriate subject data into the eCRF and randomize the subject. A study drug bottle number will be assigned to the subject based on the predetermined randomization by the EDC/IWRS system. The designated site personnel should supervise the administration of the first dose of study drug by the subject in the clinic before dispensing the assigned study drug bottle along with written dosing instructions and diary to the subject. The second dose will be administered at home.

A subject who fails to qualify for the study on POD1 will not be rescreened.

Note that the use of IOP-lowering medications or aqueous release procedures are not allowed on POD1.

Study drug dosing/administration procedures including handling bottle replacement, diary/dosing compliance and the list of treatments are presented in [Section 5.1.2](#). Subjects are reminded to bring the diary to each clinic visit in order for site staff to review dosing compliance.

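### Table 2 says subjects with corneal or scleral thinning are excluded, but no numbered eligibility criterion names thinning

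*Protocol*

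**What the plan says.** Protocol Section 1.5.1.4 lists delayed healing among the corticosteroid class risks and adds: "In those diseases causing thinning of the cornea or sclera, perforations have been known to occur with the use of topical corticosteroids". Table 2 (Section 1.5.2) answers that risk in its Delayed Healing row: "Subjects with thinning of the cornea or sclera are excluded because of the greater risk of perforations with the use of topical steroids". The statement carries no condition and no reference to a criterion.

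Section 6.2.3 sets the eligibility check on the day of randomization: "The site will review eligibility criteria ([Section 4.2](#) and [Section 4.3](#)) to determine if the subject qualifies for randomization". It continues: "If the subject meets all criteria, the subject will be randomized by site personnel using the EDC/IWRS system". Section 4.1 takes the same approach, defining the subjects to be randomized by the inclusion and exclusion criteria. Neither section sends the site to Table 2.

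**The concern.** The protocol identifies a serious harm, perforation, and says that the subjects at risk are kept out. The list that sites work from does not contain that exclusion. A site that follows Section 6.2.3 exactly could therefore randomize a subject whom the protocol elsewhere says is excluded.

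For thinning with no listed cause, the safeguard depends on each Investigator recalling Table 2 and invoking exclusion 27, and practice may differ across about 30 sites. If exclusion 27 is not invoked, no numbered criterion has been broken, so the subject would not appear in the SAP Section 7.2 listing of subjects who fail the eligibility criteria. The sponsor could not show from that listing that its stated safeguard had been applied.

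**Working it through.** The plan gives no figure to reproduce, so the check compares the texts.

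**1. Is thinning named in any criterion?**

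- Exclusion criteria 1–28 (Section 4.3 and Synopsis): 0 name it.
- Inclusion criteria 1–11 (Section 4.2 and Synopsis): 0 name it.
- Sub-study criteria 1–4 (Section 4.4): 0 name it.
- Total: 28 + 11 + 4 = 43 criteria, of which 0 name thinning. The 28 exclusions are the count that matters most, since that is where the item would be expected.

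**2. Which criteria reach it indirectly?**

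| Criterion | What it can catch | Limit |
|---|---|---|
| Exclusion 4 | Immune-related disease: "Have an immunosuppressive or autoimmune disease that in the opinion of the Investigator could affect intraocular inflammation or the normal healing process of the eye" | Investigator opinion |
| Exclusion 5 | Ocular or systemic disease affecting healing | Must be uncontrolled |
| Exclusion 10 | "History of herpes keratitis in the study eye" | That disease only |
| Exclusion 11 | Corneal abrasions or ulcers | Must be active |
| Exclusion 12 | "Have active or a history of chronic or recurrent inflammatory eye disease (e.g., iritis, scleritis, uveitis, iridocyclitis, rubeosis iridis) in the study eye" | That disease group only |
| Exclusion 13 | Ocular infections | That disease group only |
| Exclusion 14 | Corneal dystrophies, dysthyroid eye disease | Those diagnoses only |
| Exclusion 19 | Trauma with scarring or deformity | Trauma plus Investigator opinion |

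Exclusion 15 (uncontrolled, clinically significant dry eye), exclusion 17 (corneal surgery, but only in the 6 months before Screening) and inclusion 9 (no significant pathology affecting acuity) may catch a few more. Quiet disease after recurrent scleritis or herpes keratitis is covered, by 12 and 10. What is left is thinning outside these causes: for example, stable thinning with no listed diagnosis, or thinning that follows corneal surgery more than 6 months earlier and does not affect acuity. Only exclusion 27 reaches it, and that criterion applies only if the Investigator decides that it should.

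**3. How do the other Table 2 exclusions compare?**

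| Table 2 row stating an exclusion | Numbered counterpart |
|---|---|
| Intraocular pressure increase | Exclusion 9, inclusion 11 |
| Delayed healing (thinning) | None |
| Infection ("Subjects with on-going ocular bacterial, viral or fungal infections are excluded from the study") | Exclusion 13 |
| Pregnancy | Inclusion 3 and 4 |
| Hypersensitivity | Exclusion 1 |

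Four of the five legible rows have a counterpart; 5 − 4 = 1 does not. The pattern suggests an omission, not a decision.

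**4. Could redaction explain it?** In Section 4.3 only criterion 1 is blacked out, and the Synopsis shows that it concerns allergy. Section 1.5.3 (Contraindications) is partly blacked out and might mention thinning, but a contraindication there would still not be one of the criteria that Section 6.2.3 tells sites to check.

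**The case against.** The best defence is that the gap is narrow and already guarded. The listed criteria catch many of the diseases behind thinning. Table 2 is part of the same protocol, so an Investigator who has read it can exclude the rest under criterion 27. Subjects have slit-lamp examinations at Screening and POD1 and are assessed for surgical suitability. Dosing lasts 14 days, and Table 2 reports no delayed healing in CPN-201. Randomizing a subject whom Table 2 excludes could be recorded as a protocol deviation under Section 11.4 and would then be listed under SAP Section 7.2. The blacked-out part of Section 1.5.3 and the Study Reference Manual are not visible and might mention thinning. The match between Table 2 and the criteria is also imperfect elsewhere: the infection row has no eye limit, while exclusion 13 is limited to the study eye.

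Much of this stands. The affected group is probably small, a careful Investigator has a route to exclude, and a deviation could be recorded. It does not close the gap. Exclusion 27 is discretionary where Table 2 is not. Section 9.1.2 points Investigators to Table 2 only as guidance on anticipated adverse events. A deviation would be recorded only if someone recognized the Table 2 sentence as an eligibility rule. The infection row, even if imperfectly matched, has a numbered criterion that names its subject; thinning has none.

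**Conclusion.** The concern holds. An exclusion that the protocol states without qualification, and ties to a named serious harm, is missing from the criteria that govern randomization: 0 of 43 criteria name it, and it is the 1 of 5 legible Table 2 exclusions without a counterpart. The practical gap is confined to thinning with no listed cause. No exposure figure can be given, because the documents contain no prevalence. Sample size, power, type I error and the efficacy analyses are not affected. The conclusion assumes that sites apply Section 6.2.3 as written; material not available here, such as the Study Reference Manual, could prompt for thinning but would not make it a protocol criterion. The change should be made, on safety and consistency grounds.

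**What to change.** Add a numbered exclusion criterion to Section 4.3 and the Synopsis, worded for example: *Have thinning of the cornea or sclera in the study eye, as judged by the Investigator at slit-lamp examination.* Apply it at the Screening and POD1 slit-lamp examinations, and cite its number in the Delayed Healing row of Table 2. The study-eye limit is not in Table 2. It fits because only that eye is dosed and exclusion 13 carries the same limit, and the row should be aligned with it.

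Rewording Table 2 to cite only the criteria that already apply would also remove the inconsistency, but it would give up the stated protection for thinning with no listed cause.

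The cost is one criterion in two places and one cross-reference, with no new procedure, visit or analysis. A small number of otherwise eligible subjects may be lost; the documents give no basis for a figure. The criterion would still rest on ungraded judgement, because the slit-lamp items in Section 7.3.1.3 include no scale for thinning. It would, however, be a mandatory check, and a breach would appear in the SAP Section 7.2 eligibility listing.

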2.0 STUDY OBJECTIVES AND ENDPOINTS

The objectives and corresponding study endpoints are presented in Table 3 below:

Table 3: Study Objectives and Endpoints

Objectives	Endpoints

Primary Efficacy Objective
 
The primary efficacy objective is to investigate the efficacy of APP13007 versus matching vehicle placebo for the treatment of inflammation and pain through post-operative day (POD) 15 after cataract surgery in the study eye.
	
Primary Efficacy Endpoints
 
 • The proportion of subjects with Anterior Chamber Cell (ACC) Count = 0 [ACC Grade = 0] at post-operative day 8 (POD8), maintained through POD15 • The proportion of subjects with Ocular Pain Grade = 0 at POD4, maintained through POD15

Secondary Efficacy Objective
 
The secondary efficacy objective of this study is to investigate the effect of APP13007 versus matching vehicle placebo on markers of inflammation, ocular pain and visual acuity after cataract surgery in the study eye.
	
Secondary Efficacy Endpoints
 
 • Proportion of subjects with ACC count = 0 [ACC Grade = 0] at PODs 4, 8 and 15 • Proportion of subjects with Ocular Pain Grade = 0 at PODs 4, 8 and 15 • Proportion of subjects with Anterior chamber flare (ACF) Grade = 0 at POD8 maintained through POD15 • Proportion of subjects with ACF Grade = 0 at PODs 4, 8 and 15

Objectives	Endpoints
	
Mean change-from-baseline in ACC Grade at PODs 4, 8, and 15Mean change-from-baseline in Ocular Pain Grade at PODs 4, 8 and 15Mean change-from-baseline in ACF Grade on PODs 4, 8 and 15Number of subjects rescued on or prior to each visit and overallMean change-from-baseline in best corrected visual acuity by pinhole method using an Early Treatment Diabetic Retinopathy Study (ETDRS) chart at PODs 4, 8 and 15

Safety Objective
 
The safety objective is to investigate the safety and tolerability of APP13007 versus matching vehicle placebo for the treatment of inflammation and pain after cataract surgery.
	
Safety Endpoints
 
Adverse events (AEs)Best corrected visual acuity by pinhole method using an ETDRS chart from baseline to each post-surgery visitSlit-lamp biomicroscopy
Change-from-baseline in ocular signs to each post-surgery visitDilated indirect ophthalmoscopy
Change-from-baseline in ocular signs to Visit 6 (POD22)Mean changes in corneal endothelial cell density, percent hexagonality and coefficient of variation from baseline (Visit 1/Screening) to Visit 7 (POD85) in the study eye in subjects in the Endothelial Cell Sub-studyIntraocular pressure (IOP) at each visit and change-from-baseline to Visit 6 (POD22) measured with a Goldmann applanation tonometer

3.0 STUDY DESIGN

3.1 STUDY DESIGN OVERVIEW

This Phase 3 study will evaluate APP13007 in comparison to the matching vehicle placebo in a randomized, parallel-group, double-masked fashion. The subjects will have undergone routine cataract surgery on Day 0 of the study and will be assessed the next day (POD1) after uncomplicated surgery for eligibility for randomization to study treatment. The study comprises the Main Study and the Endothelial Cell Sub-study. All randomized subjects (approximately

370) will participate in the Main Study. The Endothelial Cell Sub-study will comprise a subgroup of approximately 176 subjects at study sites qualified to perform the assessment of corneal endothelial cell parameters (endothelial cell density [cells/mm²], percent hexagonality and coefficient of variation). All eligible subjects at the participating study sites for corneal endothelial cell assessment will be requested to participate in the Sub-study. If a subject is unable or unwilling to participate in the Sub-study, the Investigator has the option to enroll the subject in the Main Study only (see [Section 4.4](#) for more details).

Subjects who experience postoperative inflammation on POD1 and who meet all other eligibility criteria will be randomized to one of two study treatments (either Treatment 1 or Treatment 2) at a 1:1 ratio:

- Treatment 1: 1 drop APP13007 BID (morning and evening) for 14 days instilled to the operated study eye
- Treatment 2: 1 drop matching vehicle placebo BID (morning and evening) for 14 days instilled to the operated study eye

3.2 STUDY VISIT OVERVIEW

This study will include up to 7 scheduled clinic visits (including the surgery day) over a range of ~ 24 to ~ 51 days for the subjects in the Main Study who are not participating in the Endothelial Cell Sub-study, while subjects in the Endothelial Cell Sub-study will have up to 8 scheduled clinic visits (including the surgery day) over a range of ~ 87 to ~ 114 days.

Note:

- (i) The schedule of visits is the same for all randomized subjects from Visit 1 to Visit 6
- (ii) The study drug will be dosed BID for 14 days for all randomized subjects.

